7.4. Extraordinary Visits

If the participant presents any adverse event or relevant signs and symptoms during the study period; or if the participant needs to be evaluated before regular visits, the participant should contact the Researcher or the Researcher himself can contact the participant if necessary. In such specific cases, the Investigator's assessment will be considered as an extraordinary visit.

If the extraordinary consultation results in the withdrawal of the participant of the study, it will be considered as a closing visit and all activities related to the Final Follow-up Visit (V11) should be carried out.

7.5. Adherence

Since, for safety reasons, the experimental therapy used in the study will have the total dose divided into 3 administrations, one every 30 days, the participant who, for some eventuality, does not attend the scheduled administration dates will not be discontinued from the study, since that the disease in question is considered serious and has drug treatments only for the management of symptoms. Safety and efficacy data obtained from these participants will only be considered in the ITT population analysis.

To increase the participant's adherence to the protocol, it will be discussed with the same in what the trial consists before his/her consenting, appointments will be scheduled at convenient times, expenses such as transportation and food will be reimbursed, and the participant will be encouraged to remain in the study.

8. STATISTICAL PROCEDURES

The study data will be recorded in the medical records of the research participant and will later be transcribed to the company's electronic CRF. The data inherent to the study will be tabled and sent to the statistician responsible for the study. Statistical analyses will be performed after the resolution of all inconsistencies and performance of data quality control.

The disposition of screened participants, included in the study, who received medication, who prematurely discontinued or completed the study will be summarized by treatment dose.

Demographic characteristics, pre-existing clinical conditions, medical history, previous treatments, reported at baseline will be summarized by treatment group, considering participants who received at least one dose of the drug under test.

Graphs, tables and descriptive analyses will be carried out using an appropriate statistical system.

8.1. Sample size determination

The estimated number of participants was calculated considering clinical/regulatory and non-statistical assumptions. In this way, the document Considerations for the Design of Early-Phase Clinical Trials of Cellular and Gene Therapy Products - Guidance for Industry (FDA, 2015) predicts that a smaller sample size is considered appropriate for diseases considered fatal, where a major potential benefit may warrant an unknown risk. Additionally, considering conditions provided by the FDA document such as the still limited capacity of the investigational product manufacturing and the relatively rare prevalence of the target disease, Sponsor suggests the sample size of 35 participants, which is considered a feasible sample size and at the same time adequate to meet the proposed objective.

8.2. Analysis Populations

The analysis of the study data will be based on the following populations as described below:

8.2.1. Population Analysis of Intention to Treat (ITT)

All participants who make use of the first administration of the investigational product of the study will constitute the population of intent to treat (ITT – *intention-to-treat*).

8.2.2. Population Analysis of Intention to Treat Efficacy (ITTe)

All ITT participants who have made at least one efficacy assessment.

8.2.3. Population Analysis Per Protocol (PP)

All participants who, according to the protocol guidelines, do not present major deviations, will constitute the population per protocol (PP - per protocol).

Major protocol violations will be reviewed before data analysis begins.

8.2.4. Safety Analysis Population

All participants who receive at least one administration of the investigational product of the study shall be included in the safety analysis population; identical to the ITT population.

8.3. Measurement of the primary variable

For the evaluation of the best dose-response, the score in the evaluation of the UHDRS scale (*Unified Huntington's Disease Rating Scale*) was defined as the primary outcome.

The evaluation of the primary variable will be performed considering the total result of the UHDRS scale. There will also be the evaluation of the composite UHDRS scale (cUHDRS).

The reports will include analyses of the values at the time of inclusion (V-3) in relation to the end of treatment (V11), as well as the analysis of the values of the uniformization period (mean values of visits V-3, V-2 and V-1) in relation to the end of treatment (V11).

The CAP score refers to the term in English *CAG - Age Product (CAP)*, which is an index calculated in relation to age and length of CAG repetition. This score will be used in order to complement the measurement of the primary variable, so that the participant's age and CAG repetition are taken into account in the analysis of the results over time.

The CAP score formula is: CAP= {100 x Age (CAG -L)}/ S

CAG being the number of repetitions on chromosome 4 (consider the allele with the highest numbering), L and S are constant (L=30 and S=627). In which "L" is a scale constant that anchors the length of the CAG approximately at the lower end of the distribution relevant to the pathology of HD. And "S" is a normalization constant chosen so that the CAP score is approximately 100 at the expected onset age of the patient, as estimated by Langbehn et al. 2004. For the calculation in this study, the Value of S used will be S = 627, which are estimates obtained by a reanalysis of the data of Langbehn et al presented by Warner and Hayden 2012.

8.4. Measurement of secondary variables

Secondly, the safety as well as preliminary evidence of efficacy of the Cellavita-HD investigational product will be evaluated through of the following variables

a) Check for clinical neurological improvement throughout the study:

The UHDRS scale will be evaluated at each visit to measure neurological improvement.

b) Check the overall improvement in disease severity by the CIBIS scale throughout treatment:

The profile of the CIBIS scale will be considered for the evaluation of the overall clinical improvement of the participant through the treatments of the study.

c) BMI assessment:

BMI (Body Mass Index) will be evaluated through BMI profiles obtained during treatment.

d) Evaluate the suicide domain of the HAM-D scale throughout treatment:

It will be evaluated especially the domain "Suicide" by means of classification scores, in which scores of 8 – 13 correspond to mild depression, 14 – 18 to moderate, from 19 - 22 to severe and above 23 points to very severe depression. The "suicide" domain of the HAM-D scale will be evaluated through the profiles obtained throughout the treatment.

e) Neurological evaluation by magnetic resonance imaging of the brain:

It will be assessed through the profiles obtained during the treatment of the following measures:

- Cortical thickness measurements;
- Volumes of the various brain structures, especially the core of the base, with special attention to the caudate;
 - Identifiable metabolic changes in proton spectroscopy.

8.5. Measurement of the Safety Variable

During the study, the safety of the investigational product will be thoroughly assessed based on periodic evaluations including clinical, laboratory and imaging tests, so that any alteration is properly recorded. The safety data described below will be collected and recorded in the clinical file:

- Adverse events: all adverse events will be monitored and reported in the clinical form of the study from the signature of the Informed Consent, including type, frequency, intensity, seriousness, severity, action taken and relationship with the investigational product of the study. The adverse events may be reported by the research participant or observed by the Researcher. Adverse events will be standardized by the Investigator.
- Changes in vital signs, clinical examination and medical evaluations;
- Changes in laboratory or serology tests:
- Change in electrocardiogram (ECG);
- Incidences and classification of benign and malignant neoplasms.

The results obtained will be presented through the proportion of adverse events that occur, segmented by dose of the investigational product. Any clinically significant abnormalities that persist until the end of the study will be monitored by the Principal Investigator until resolution or until a clinically stable outcome.

8.6. Study hypotheses

8.6.1. Primary Hypothesis

Identify the dose of the Cellavita-HD investigational product that presents the best response.

8.6.2. Secondary hypotheses

Cellavita-HD is safe after intravenous administration in participants with Huntington's disease and provides evidence of efficacy in relation to the parameters evaluated.

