8.7.1.1.3. Analysis of the safety hypothesis

The safety assessment will be performed at the end of each cycle and will be verified through the incidence of reports that adverse events occurred during the study, in relation to causality with the treatment under study.

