#### 5. Statistical Hypothesis

This study is a Phase II study to determine efficacy and safety of Cellavita HD. Hypothesis tests for efficacy will be conducted as described below. No hypothesis testing will be performed on any safety data.

All hypothesis tests will be at the two-sided 5% significance level (Two-sided Type I error of 0.05)

H0: There is no difference in rate of change (slope) per year from Baseline through V11 in TMS between the two pooled active treatment groups and the placebo group

Ha: There is a difference in rate of change (slope) per year from Baseline through V11 in TMS between the two pooled active treatment groups and the placebo group

The following statistical tests will be performed:

- 1. Between the two active pooled treatment groups and placebo (primary)
  Participants receiving either 1 million or 2 million cells per kg (Treated) vs. Placebo
- Between each of the two active treatment groups individually and placebo (to determine efficacy of each treatment group compared to placebo)
   Participants receiving 1 million cells per kg (Treated) vs. Placebo
   And Participants receiving 2 million cells per kg (Treated) vs. Placebo
- 3. Between the two active treatment groups to assess similarity between the two treatment groups.

F-SA-06-01, Version 5.0/30 Dec 2021, SOPs Link: SOP-SA-06

Participants receiving 1 million vs. 2 million cells per kg.

The same tests performed for TMS will also be performed for other continuous endpoints.

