#### 7. Statistical Methods

#### 7.1. General Statistical Consideration

All analysis (generation of Tables, Figures and Listings) will be performed using SAS 9.4 or newer.

All statistical Tables will summarize data by the following columns (or rows when summary Table is by treatment groups in rows) Low Dose, High Dose, Low & High Dose, Placebo, Total. If there are space limitations the Total column can be excluded. A footnote will clarify what Low and High Dose refer to.

All data collected on the eCRF will be included in the Listings. Some data will only be in Listings and no summary Tables or Figures will be created.

The eCRF collected participant initials and date of birth (The concatenation of these is variable SUBNUM in the dataset). For participant privacy this data will not be included in any Tables or Listings but will be retained in the analysis database. The Site ID and internal ID will be used to create a new unique Participant ID. In Listings this new Participant ID will be used as the unique identification of participants in this study.

Descriptive statistics for continuous data will include the mean, standard deviation, median, minimum, maximum, Q1, Q3.

Categorical data will be summarized by the frequency and percentages within each category. Unless otherwise specified the denominator for the %'s will be the number of participants randomized to the treatment group within the population summarized. Wherever applicable missing data will be summarized as a category.

F-SA-06-01, Version 5.0/30 Dec 2021, SOPs Link: SOP-SA-06

Sponsor: Cellavita Pesquisa Científica Ltda.

Protocol: ADORE-DH

All summary statistics will be displayed to 1 decimal place unless the data recorded is only at the decimal level in which case summary statistics will display data at one additional decimal place. Summary statistics such as minimum or maximum will be displayed as an integer or to the accuracy of data collected if it is only at the decimal level.

The p-value will be displayed up to 4 decimal places. If the p-value is less than 0.0001, it will be presented as' <.0001'; if the p-value is greater than 0.9999, it will be presented as '>.9999'.

Baseline will be defined as the last non-missing measurement before a participant received first treatment of study drug (At baseline visit of V0).

All descriptive statistical summaries and statistical inferences will be performed based on nominal visits (visits at which data are collected).

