#### 7.5.2. Adverse Events

Analysis of Adverse Events will be performed based on the safety population. All Adverse events will be coded using MedDRA ver. 24.1 Sept 2021

Statistical summaries will be performed on general incidence rate of treatment emergent adverse event (TEAEs) including number of events and number of participants with the events. In summarizing the number of participants with adverse events, if a participant has more than one event within the SOC (or PT) they will only be counted once in that row.

The terms Treatment Emergent Adverse Events (TEAEs) and Adverse Events (AEs) are used interchangeably below and unless otherwise specified refer to TEAEs.

Adverse Events will be summarized in the following Tables:

- Overall one page summary of TEAEs.
- Summary of TEAE's by SOC & PT sorted by total number of participants with the TEAE within a SOC and within SOC by total number of participants within a PT. This sort order will also be used in other Tables by SOC and PT indicated below.
- Summary of Severe TEAE's by SOC & PT.

- Summary of TEAE's by SOC, PT and Maximum Severity within SOC or PT. The order for displaying severity will be: Mild, Moderate, Severe.

- Summary of TEAE's Related to Study Drug by SOC PT. For this Table any AE's classified as Certain, Probable/Likely, Possible will be included.
- Summary of TEAE's by SOC, PT and Maximum Relationship to Study Drug within SOC or PT. The order for displaying Relationship to Study Drug will be: Conditional/Unclassified, Unlikely, Possible, Probable/Likely, Certain,.

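### The protocol keeps product safety as a hypothesis to be verified, but no interval or estimated difference from placebo is planned for any adverse-event result at 14, 14 and 7 participants.

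*Protocol*

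**What the plan says.** **Protocol.** Section 8.6.2 includes, as a secondary hypothesis, that "Cellavita-HD is safe after intravenous administration in participants with" Huntington's disease. Section 8.7.1.1.3, the dedicated analysis of that hypothesis, says safety "will be verified through the incidence of reports that adverse events occurred during the study", read in relation to causality. Section 8.5 says results are "presented through the proportion of adverse events that occur, segmented by dose of the investigational product". None of the three gives an acceptable rate, a margin, an interval or an estimated difference from placebo.

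**SAP.** Section 2 words the safety objective as evaluating the incidence and classification of adverse events. Section 5 states "No hypothesis testing will be performed on any safety data". Section 7.1 says "Categorical data will be summarized by the frequency and percentages within each category", under the columns "Low Dose, High Dose, Low & High Dose, Placebo, Total". Section 7.5.2 plans incidence summaries "including number of events and number of participants with the events", broken down by system organ class, preferred term, severity and relationship to treatment. The only 95% intervals in the SAP are those for the efficacy model in 7.4.1, and Fisher's test in 7.4.2 is also for efficacy.

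SAP 7.6 says its analysis replaces the protocol's. It does not withdraw or reword the protocol's safety hypothesis, and SAP section 5 still describes the study as one to determine both efficacy and safety.

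**The concern.** A hypothesis that a product is safe, verified through incidence alone, has no stated result that would contradict it. The SAP removes testing, which is reasonable at this size, but puts no measure of precision in its place. The final report would then hold bare percentages from arms of 14, 14 and 7, next to a protocol hypothesis that those percentages are supposed to verify. One placebo event appears as 1/7 = 14.3%. One event in a dose arm appears as 1/14 = 7.1%, which looks like half the placebo rate.

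This matters for what follows the trial. The protocol's justification (section 2) seeks a dose that is both maximally effective and considered safe, and says the next studies can begin once a dose is identified. Section 9.5 concedes that the safety of this class of cell therapy is not yet fully understood.

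**Working it through.** **Inputs from the documents.** Allocation 2:2:1 of 35 (protocol 6.4): 35 × 2/5 = 14, 35 × 2/5 = 14, 35 × 1/5 = 7, so the stated arm sizes reproduce. Pooled active = 28. Protocol 8.1 says the sample size rests on non-statistical grounds, so there is no planned safety precision to reproduce. The documents give no adverse-event rates. Every rate used in steps 2 and 3 is an assumption, shown over a range.

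**1. What zero events leaves open.** The Clopper-Pearson two-sided 95% upper limit for 0/n is 1 − 0.025^(1/n).
- n = 14: 1 − 0.025^(1/14) = 23.2%
- n = 28: 1 − 0.025^(1/28) = 12.3%
- n = 7: 1 − 0.025^(1/7) = 41.0%

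This step needs no assumed rate.

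**2. How often a clean table arises.** P(no participant with an event) = (1 − p)^n.

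| Assumed true risk p | 14 in one dose arm | 28 pooled |
|---|---|---|
| 5% | 0.95^14 = 48.8% | 23.8% |
| 10% | 0.90^14 = 22.9% | 5.2% |
| 15% | 0.85^14 = 10.3% | 1.1% |

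**3. How often the active percentage is no higher than placebo's although the true risk is doubled.** Exact enumeration of two independent binomials, with 7 on placebo:

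| Assumed active vs placebo risk | One dose (14): tied or lower | of which strictly lower | Pooled (28): tied or lower | of which strictly lower |
|---|---|---|---|---|
| 10% vs 5% | 42.0% | 19.3% | 30.2% | 22.3% |
| 20% vs 10% | 32.1% | 18.5% | 25.7% | 18.7% |
| 40% vs 20% | 20.3% | 12.2% | 15.4% | 11.6% |

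**4. What a risk-difference interval would show.** The Newcombe interval combines the Wilson limits (l, u) of the two proportions. With d = p1 − p2, the lower limit is d − √[(p1 − l1)² + (u2 − p2)²] and the upper limit is d + √[(u1 − p1)² + (p2 − l2)²].

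- 0/14 vs 0/7: the Wilson upper limit for 0/n is z²/(n + z²), with z² = 3.84. That gives 3.84/17.84 = 21.5% and 3.84/10.84 = 35.4%. Difference 0, 95% CI −35.4 to +21.5 points.
- 0/28 vs 0/7: 3.84/31.84 = 12.1%. Difference 0, 95% CI −35.4 to +12.1 points.
- 1/14 vs 1/7: Wilson limits 1.3% to 31.5% and 2.6% to 51.3%. Difference −7.1 points. Lower limit −0.071 − √(0.059² + 0.370²) = −44.6 points. Upper limit −0.071 + √(0.243² + 0.117²) = +19.9 points.
- 3/14 vs 0/7: difference +21.4 points, 95% CI −16.6 to +47.6.

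So the table that looks favourable (1/14 vs 1/7) remains compatible with an excess of about 20 points on active.

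**5. Why p-values would not help.** With 0/7 on placebo, two-sided Fisher significance at 5% needs at least 7/14 in one dose arm or 13/28 pooled. For the 20% vs 10% case, power is 0.6% with 14 vs 7 and 0.1% with 28 vs 7.

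**The case against.** The strongest reply is that the governing document already treats safety properly. The SAP supersedes the protocol's analysis, frames safety as evaluating incidence, confines its formal hypotheses to efficacy and rules out safety testing. Descriptive safety reporting is ordinary in a 35-person phase II trial, and since counts and denominators will be tabulated, a reader can compute the bounds. Most of this stands. It reduces the point to a loose protocol hypothesis plus missing precision. It does not remove it, because the hypothesis is never withdrawn and no planned table states the uncertainty.

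Three stronger readings are tempting but unsupported:

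- **That a clean or reversed table would be declared proof of safety.** No section says so and no decision rule exists. Such a table could be read that way, and the protocol's verification wording invites it. Protocol 10.8 itself says exploratory studies have marked statistical limits and are not built for final conclusions.
- **That there is no comparison with placebo.** Placebo has its own table column, events are broken down by severity and relationship, and laboratory, ECG and vital-sign results get change summaries or shift tables. What is absent is an estimated difference or an interval.
- **That no adverse-safety criterion exists.** Protocol 9.6.2 pre-specifies rules for interrupting the study. They act on the conduct of the trial and do not evaluate the hypothesis in 8.6.2, but they are real safeguards.

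It is also fair to object that the rates in steps 2 and 3 are illustrative and that the 32.1% figure includes ties. The strictly reversed share is 18.5%. Step 1 depends on neither.

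**Conclusion.** The point holds as a modest one. The protocol keeps a positive safety hypothesis to be verified through incidence, and neither document plans an interval or an estimated placebo difference for any adverse-event result. At these arm sizes an event-free dose arm does not exclude a true risk of up to 23.2%, and an event-free pooled active group does not exclude up to 12.3%. Those bounds assume only that all randomised participants are dosed and observed; fewer would widen them. The chance of a misleadingly favourable table when risk is doubled runs from about 15% to 42% across the assumed rates.

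Nothing here biases a result or makes an analysis impossible, and keeping safety descriptive is not itself a fault. What is limited is the conclusion the trial can draw about safety. This is a cheap improvement to reporting.

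**What to change.** In SAP 7.5.2, for participants with any, severe, serious and related treatment-emergent events:

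1. Report exact (Clopper-Pearson) 95% intervals for each arm and for pooled active, including where the count is zero.
2. Report the risk difference of each dose and of pooled active versus placebo with a 95% interval, for example Newcombe, and no p-values.
3. Add an explicit summary row for serious events. The listed tables include none, and the contents of the one-page overall summary are not specified.

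State in the SAP and the study report that safety is estimated and not verified, and that the absence of an observed excess is not evidence of safety at this size. If the protocol is amended, bring 8.6.2 and 8.7.1.1.3 into line with the SAP's safety objective.

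The cost is a few table columns, one row and a less favourable safety statement, with no new data. The protocol rewording is best left to an amendment made for other reasons: section 11.2 gives changes to the statistical analysis plan as an example of a substantial amendment needing ethics review, and SAP 4.1.2 already describes the final-visit MRI in the past tense. The same section bears on how the SAP additions are filed, so the sponsor should settle that. If they are made after unblinding, they should be labelled as such.
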